3.2.4 History of hypersensitivity to perflutren

3.2.5 History of pulmonary hypertension

3.2.6 Patients who are pregnant or are trying to become pregnant

3.3 Informed Consent Process

All participants will be provided a consent form describing the study with sufficient information for participants to make an informed decision regarding their participation. Participants will sign an IRB approved informed consent prior to participation in any study specific procedure. The participant will receive a copy of the signed and dated consent document. The original signed copy of the consent document will be retained in the medical record or research file.

3.4 Randomization Procedures

This is an open label study.

3.5 Study Timeline

Definity®-enhanced ultrasound at baseline will be completed prior to delivery of SABR treatment. The patient will then be re-scanned 0-7 days post their first fraction of radiation treatment. An additional US scan will be performed 2-4 months (when patient comes to routine follow-up CT and PET-CT imaging).

Primary Completion:

The expected study completion timeline is within 24 months from when the study opens.

Study Completion:

The expected study completion timeline is within 24 months and 1 day from when the study opens.

4 TREATMENT PLAN

Pregnancy Test

If the subject is female and of child-bearing potential, exclude the possibility of pregnancy by:

- testing serum β HCG or urine pregnancy test prior to the start of Definity® administration (the local laboratory may be used)
- obtaining surgical history (e.g., tubal ligation or hysterectomy)
- obtaining medical history (post-menopausal with a minimum of 1 year without menses).

See Appendix B.

Safety Assessments Adverse Events

We will record all untoward medical events in the Adverse Event section of the CRF. Only post-dose untoward medical occurrences will be tabulated as adverse events.

Imaging Procedures

The unenhanced ultrasound and Definity®-enhanced images will be performed, in the same session, using commercially available (FDA-approved) ultrasound systems with appropriate contrast-specific capabilities. The ultrasound examination, both unenhanced and contrast-enhanced should be performed by qualified personnel with at least 3 years of experience in liver ultrasound or Fellows with appointment in Stanford Radiology

Definity® will be administered intravenously into a central line or port or an upper extremity vein (e.g., a vein in the cubital fossa or dorsal aspect of the wrist or hand) using a catheter while observing aseptic technique. Immediately following the Definity® injection, 5 mL to 10 mL of saline will be administered to flush the intravenous line of any remaining contrast agent. Subjects will be monitored for any untoward medical occurrences listed in a study case report form or note for 30-60 min after Definity® injection is initiated.

Imaging parameters:

Contrast-specific imaging will be performed with an abdominal matrix-array transducer (PM mode, Philips iU22 with X6-1; Philips Ultrasound, Bothell Wash) which is a low-mechanical-index (MI) nonlinear imaging (MI, 0.06) that allows visualization of the micro-bubbles nondestructively. Time-gain controls will be aligned to the center line. Receive gain, dynamic range, image depth, and transmit focus will be optimized for each patient at the baseline examination, and then identical settings will be used at follow-up. Disruption-replenishment data will be collected for approximately 30 seconds following 1-second, 8-frame flash at an MI of 1.3.

Unenhanced Ultrasound

During the unenhanced ultrasound examination, the morphology and localization of the target FLL will be evaluated using gray scale ultrasound and color/power Doppler modes. The target lesion will be identified using gray scale ultrasound and its location will be identified using Coineaud's system. Then, either color Doppler imaging or power Doppler imaging should be used to study the morphology/vascularity of the target lesion and surrounding parenchyma. Specific measurements with Spectral Doppler may be used depending on the presence and/or visualization of vessels.

Contrast-Enhanced Ultrasound Examination

The following protocol will be used, according to published literature (23):

An infusion of 1.3 mL of Definity diluted in 50 mL of saline will be administered using an injection pump. Two minutes will be allowed for the infusion to reach a steady level before disruption-replenishment. Measurements will be performed two times (to assess reproducibility of the replenishment curves analysis following microbubble destruction and replenishment of microbubbles into the US field-of-view).

4.1 General Concomitant Medication and Supportive Care Guidelines

Concomitant Medications

Given that concomitant meds are neither indicated nor no counter-indicated as per the Definity Prescription Information the Concomitant Medication section of the Case Report Form (CRF) will not be filled.

4.2 Criteria for Removal from Study

Subject will be discontinued from the study if the subject:

- withdraws consent.
- during the course of the study manifests condition matching exclusion criteria.
- will not be able to adhere to protocol timeline due to scheduling or other conflict
- has an adverse event that, in the opinion of the Investigator, requires the subject's Discontinuation.

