2.4 Study Design

For clinicaltrials.gov and Stanford Clinical Trials Directory compliance

This is a pilot, single-center study in subjects with liver tumors. The primary objectives of this prospective pilot study is to (1) determine the feasibility and reproducibility of 3D contrast

enhanced ultrasound imaging in liver cancer patients undergoing Stereotactic Ablative Radiotherapy and (2) evaluate whether there are treatment induced early changes in imaging metrics derived from 3D contrast enhanced ultrasound. This study will provide valuable insight as to the potential of baseline and/or early post-treatment 3D ultrasound perfusion characteristics (measurements of blood-flow) of primary and metastatic liver tumors to predict tumor response to Stereotactic Ablative Radiotherapy.

The target lesion will be located at the simulation CT scan for treatment planning. Prior to Definity® administration, gray scale and Doppler (color or power imaging) ultrasound investigations of the target lesion will be performed using commercially available ultrasound equipment and standard techniques (B-mode or Harmonic imaging) to study the anatomy of the target lesion and surrounding parenchyma.

Immediately after the unenhanced ultrasound evaluation, contrast-enhanced ultrasound will be performed, according to the procedures described to study the lesion vascularity in comparison to the surrounding parenchyma. Definity® will be administered intravenously through a central line or in a peripheral vein.

Unenhanced ultrasound and Definity®-enhanced ultrasound images will be recorded and stored anonymously.

The primary analysis will be based on comparison of the readout (perfusion parameters of the lesion) at baseline, at 0-7 days after the first fraction of radiotherapy treatment, 2-4 months following the start of radiotherapy, and the clinical outcome of the patient, including findings on routine CT and PET-CT imaging.

This is a Single Group, Open Label Study designed to evaluate to evaluate as a primary outcome feasibility and efficacy.

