- Histogram analysis and summary statistics (mean, median, variance, and maximum) of the relative changes (difference/average) of repeated 3D DCE-US measures. (Small variance and zero mean of the relative changes will be indicative of highly reproducible 3D DCE-US measures).
- Histogram analysis and summary statistics (mean, median, variance, and maximum) of the relative changes (difference/baseline) in 3D DCE-US measures before and after SABR. Large mean differences will be indicative of treatment (SABR) effect.

- Calculation of proportion of 3D DCE-US examinations in which fusion to CT is possible with tracking of the ultrasound transducer. Calculation of proportion of 3D DCE-US examination in which repeated scans is successful. These proportions are metrics of feasibility (target 80%-90%). Successful fusion to CT in particular is important metric is 3D DCE-US is to be explored as add-on imaging for treatment planning in further studies.

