12.5 Sample size justification

This study is an exploratory study and there is currently not sufficient information to perform a sample size calculation.

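### Section 4.2 removes from the whole study a patient who cannot keep the scan timeline, so a missed 0-7 day scan can also forgo the 2-4 month scan

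*Combined protocol and SAP*

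**What the plan says.** Section 4.2 opens its list of removal criteria with "Subject will be discontinued from the study if the subject" and includes the subject who "will not be able to adhere to protocol timeline due to scheduling or other conflict". The consequence is leaving the study, not missing one visit. The only criterion in the list left to judgement is the adverse-event one: "has an adverse event that, in the opinion of the Investigator, requires the subject's Discontinuation".

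Section 3.5 sets the timeline. After a baseline scan, "The patient will then be re-scanned 0-7 days post their first fraction of radiation treatment". The late scan is tied to a visit outside the study: "An additional US scan will be performed 2-4 months (when patient comes to routine follow-up CT and PET-CT imaging".

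Section 2.4 uses both post-treatment scans: "The primary analysis will be based on comparison of the readout (perfusion parameters of the lesion) at baseline, at 0-7 days after the first fraction", and it goes on to name the 2-4 month readout and clinical outcome. Section 12.3 summarises "relative changes (difference/baseline) in 3D DCE-US measures before and after SABR" without saying which post-treatment scan is meant. It also sets a feasibility target of 80%-90% for proportions counted over examinations.

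No section separates a missed scan from withdrawal, provides for an out-of-window scan, replaces patients, defines an analysis set, or says how missing scans are handled.

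**The concern.** The change from baseline to 2-4 months needs a baseline scan and a late scan. It does not need the early one. Yet a patient who cannot attend between day 0 and day 7 meets a mandatory removal criterion, and the late scan is then not acquired, even though the patient may be on site for routine imaging anyway.

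Three things are lost with that scan: one baseline-to-late change, one pair of repeat acquisitions for reproducibility, and one CT-fusion attempt. The late group is also restricted, by construction, to patients who kept the early window.

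Feasibility is touched too. It is a primary objective, and difficulty in attending is part of the answer. A removed patient contributes no later examinations, so proportions counted over examinations performed would leave those scans out. Section 12.3 says the results will help to size later studies, so avoidable loss from a group of 20 has some cost.

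**Working it through.** **No figure to reproduce.** Section 12.4 gives 20 patients. Section 12.5 states: "This study is an exploratory study and there is currently not sufficient information to perform a sample size calculation". There is no stated dropout rate, standard deviation (SD) or effect size, so the following is an illustration.

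**Inputs.** N = 20 (section 12.4) and three planned scans per patient (section 3.5). Three quantities are assumed:
- m, the chance of missing the early window and being removed: 10%-20%
- l, the independent chance of missing the late scan for another reason: 0 or 10%
- d, the difference in mean late change between patients who keep and who miss the early window: 0.5-1.0 SD

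**Late pairs.** With the rule, pairs = N(1 - m)(1 - l). If the patient stays on study, pairs = N(1 - l). The 95% CI half-width, in SD units, is t(0.975, n - 1)/sqrt(n). With l = 0:

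| m | Late pairs, rule | Late pairs, patient kept | SE ratio | Half-width, rule | Half-width, patient kept |
|---|---|---|---|---|---|
| 10% | 18 | 20 | sqrt(20/18) = 1.054 | 0.497 | 0.468 |
| 20% | 16 | 20 | sqrt(20/16) = 1.118 | 0.533 | 0.468 |

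With l = 10%, there are 18 pairs if patients are kept, against an expected 16.2 (m = 10%) or 14.4 (m = 20%) under the rule.

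**Chance that at least one patient is lost this way.** 1 - (1 - m)^20 = 88% at m = 10% and 99% at m = 20%. At m = 5% it is still 64%.

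**Early pairs.** N(1 - m) = 18 or 16, the same with or without the rule, because a patient without the early scan cannot enter that comparison.

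**Scans acquired (l = 0).** Planned: 3 x 20 = 60.
- Under the rule: 20 + 18 + 18 = 56 (m = 10%) or 20 + 16 + 16 = 52 (m = 20%)
- With patients kept: 20 + 18 + 20 = 58 or 20 + 16 + 20 = 56

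The rule therefore costs 2 to 4 scans. A proportion taken over examinations performed has a denominator of 56 or 52 and does not show the 4 or 8 planned scans that were not done.

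**Selection.** If the two groups differ by d, the observed late mean is shifted by m x d: 0.05-0.10 SD at m = 10% and 0.10-0.20 SD at m = 20%. The documents support no value or sign for d.

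**The case against.** **The wording is ambiguous.** The criterion speaks of the timeline, not of a single visit, and is phrased prospectively. It may be meant for someone who cannot follow the schedule at all. That reading is open, but the text does not state it, and the plain words also cover a patient who cannot make days 0-7. The ambiguity is itself a reason to amend.

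**The main aim is untouched.** Objective (2) concerns early change, and section 1.1 names 0-7 days as the underlying goal. That comparison has the same patients either way. This stands and confines the point to the late scan and the feasibility counts.

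**Misses may be few.** The early window is anchored to the first fraction, so a delayed radiotherapy start moves the window with it. No section gives a miss rate. The calculation also assumes, when l = 0, that every removed patient would have attended the late scan. Both limits stand.

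**Little depends on the late mean.** The study is an exploratory pilot with descriptive summaries, and no test or decision threshold uses the late change. This stands and keeps the point moderate.

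**Stronger readings to avoid.** A reader might infer that the rule throws away data in hand. Nothing says so: the late scan is not acquired, and the baseline scan with its repeat pair remains available. A reader might also infer that the remaining patients are the fitter ones, since ECOG 0-3 is eligible. But the trigger is a scheduling or other conflict, and the documents do not link that to health. Nor is safety follow-up clearly lost, since section 7.2.1 already extends serious adverse event reporting to 30 days after the last dose.

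**Conclusion.** The point holds in a limited form. Followed as written, section 4.2 can remove a patient over one missed early scan and so forgo a usable 2-4 month scan that section 2.4 places in the primary analysis. No other section softens this.

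The cost falls on the baseline-to-late change, that scan's repeat pair and fusion attempt, and the completeness of the feasibility proportions. On an assumed 10%-20% miss rate it is 2 to 4 of 20 late pairs and a standard error about 5%-12% larger. Both figures rest on that assumption and on the removed patients otherwise attending the late scan. The late group is selected on having kept the early window, but whether this biases the late change, in which direction and by how much cannot be determined from the documents. The documents do not support a claim that the whole before/after comparison is compromised.

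The change is worth making because it is cheap and removes an avoidable loss from a small study.

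**What to change.** Amend the scheduling item in section 4.2 so that a missed or out-of-window scan is recorded as a missed visit or deviation, with its date and reason. State that the patient stays on study for the remaining scans unless another 4.2 criterion applies. The consent, exclusion-condition and adverse-event criteria stay as they are.

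In section 12.3, state that the late change is summarised in all patients with a baseline and a late scan, and report scans completed out of scans planned beside the examination-based proportions.

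The cost is a short amendment and a reason field on the case report form. The small downside is that some patients will have incomplete scan sets, which summaries of available pairs can accommodate if the number of pairs is shown for each comparison.

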5 INVESTIGATIONAL AGENT/DEVICE/PROCEDURE INFORMATION

5.1 Investigational Agent/Device/Procedure

DEFINITY® Vial for (Perflutren Lipid Microsphere) Injectable Suspension is Lantheus Medical Imaging Inc.'s non-blood based ultrasound contrast agent approved by the United States Food and Drug Administration (FDA). DEFINITY® is the first approved ultrasound contrast agent in the U.S. that offers flexible dosing and administration through IV bolus injection or continuous IV infusion. (21)

The FDA has approved activated DEFINITY® for use in patients with suboptimal echocardiograms to opacify the left ventricular chamber and to improve the delineation of the left ventricular endocardial border.

DEFINITY® is comprised of lipid-coated microspheres filled with octafluoropropane gas. DEFINITY® does not contain any human or animal materials. The microspheres contained in DEFINITY® have a mean diameter of 1.1 to 3.3 microns (in vitro measurements). The microspheres are stable and small enough to pass through the pulmonary capillaries. (21,22, 23)

The safety of DEFINITY® is well documented in multiple clinical trials involving over 1,700 patients at more than 20 U.S. medical centers. Age, gender, race and ethnicity did not affect the overall incidence of adverse events.

The overall incidence of treatment-related adverse events was 8.4%. The most frequently reported treatment-related adverse experiences were in the Central and Peripheral nervous system (3.1%), Body as a Whole (2.4%) and Gastrointestinal system (1.8%). The most frequently reported treatment-related adverse experiences were:

Headache	2.3%
Back/renal pain	1.2%
Flushing	1.1%
Nausea	1.0%

In clinical trials, serious cardiopulmonary events occurred in 19 (1.1%) patients. None of these events, which included 8 deaths and 11 other serious adverse events, was attributed to DEFINITY®, but to progression of underlying disease.

CONTRAINdications

DEFINITY® is not to be administered in patients with known or suspected right-to-left, bi-directional or transient right-to-left cardiac shunts, by intra-arterial injection, or to patients with known hypersensitivity to perflutren. In post marketing use, rare but serious cardiopulmonary or anaphylactoid reactions have been reported during or shortly following perflutren-containing microsphere administration. The risk for these reactions may be increased among patients with unstable cardiopulmonary conditions. It is not always possible to reliably establish a causal relationship to drug exposure due to the presence of underlying cardiopulmonary disease. Thus all patients need to be assessed for the presence of any condition that precludes DEFINITY® administration and it is recommended that resuscitation equipment and trained personnel are readily available.

Devices:

In addition, there will be an Optical and Electromagnetic tracking tools attached to the Ultrasound Transducer that will not be in contact with the patient. There is very little risk to the patient associated with optical tracking as there is no transfer of energy to the patient. With electromagnetic tracking there may be electromagnetic interference with implantable devices such as pacemakers, etc. Electromagnetic tracking will not be used (Optical tracking only) if the patient has an implantable medical device to eliminate risk from electromagnetic interference.

5.2 Availability

Definity is available from the Hospital Pharmacy.

5.3 Agent Ordering

Definity® is FDA approved and routinely used for patients with suboptimal echocardiograms to opacify the left ventricular chamber and to improve the delineation of the left ventricular endocardial border. It may be requested from the central hospital pharmacy with a signed physician order for the subject with the quantity to dispense. It may also be bought from the central hospital pharmacy for storage within the department of Radiation Oncology.

5.4 Agent Accountability

Central pharmacy will deliver Definity® to the Department of Radiation Oncology, where it will be stored in a temperature controlled refrigerator in the locked office of Protocol Director, [name]. The study coordinator (ACRC) will keep both a temperature log and dispensing log according to IDS standards next to the refrigerator. All subjects will be entered into OnCore.

6 DOSE MODIFICATIONS

There are no dose modifications planned for this study.

7 ADVERSE EVENTS AND REPORTING PROCEDURES

7.1 Potential Adverse Events

The safety of DEFINITY® is well documented in multiple clinical trials involving over 1,700 patients at more than 20 U.S. medical centers. Age, gender, race and ethnicity did not affect the overall incidence of adverse events.

The overall incidence of treatment-related adverse events was 8.4%. The most frequently reported treatment-related adverse experiences were in the Central and Peripheral nervous system (3.1%), Body as a Whole (2.4%) and Gastrointestinal system (1.8%). The most frequently reported treatment-related adverse experiences were:

Headache	2.3%
Back/renal pain	1.2%
Flushing	1.1%
Nausea	1.0%

In clinical trials, serious cardiopulmonary events occurred in 19 (1.1%) patients. None of these events, which included 8 deaths and 11 other serious adverse events, was attributed to DEFINITY®, but to progression of underlying cardiovascular disease.

7.2 Adverse Event Reporting

7.2.1 Adverse Events

Adverse events will be assessed for 30-60 minutes after each injection of Definity®.

Adverse events will be graded according to CTCAE v4.0. Both Serious and Non-Serious Adverse Events will be clearly noted in source documentation and listed on study specific Case Report Forms (CRFs). The Protocol Director (PD) or designee will assess each Adverse Event (AE) to determine whether it is unexpected according to the Informed Consent, Protocol Document, or Investigator's Brochure, and related to the investigation. All Serious Adverse Events (SAEs) will be tracked until resolution. SAEs must be reported while on study and up to 30 days after the last dose of the study treatment is given.

SAEs CTCAE Grade 3 and above, and all subsequent follow-up reports will be reported to the Stanford Cancer Institute Data and Safety Monitoring Committee (DSMC) using the study specific CRF regardless of the event's relatedness to the investigation. Following review by the DSMC, events meeting the IRB definition of 'Unanticipated Problem' will be reported to the IRB using eProtocol within 10 working days of DSMC review, or within 5 working days for deaths or life-threatening experiences.

7.2.2 AE Definition

An adverse event (AE) is any untoward medical occurrence in a subject or a clinical trial subject administered a medicinal product and which does not necessarily have to have a causal relationship with the use of the product.

Any untoward medical occurrence that occurs outside the period of subject follow-up defined in the protocol is not required to be collected in the AE section of the CRF.

An existing condition, which is detected by the diagnostic procedure conducted to test the efficacy of an investigational contrast agent, is not considered an AE.

Symptoms or medically significant laboratory or instrumental (e.g., electrocardiographic) abnormalities of a pre-existing condition, such as cancer or other disease, should not be considered an AE. However, occurrence of new symptoms, laboratory or instrumental abnormalities, as well as worsening of pre-existing ones, are considered AEs.

A serious adverse event (SAE) is defined as any untoward medical occurrence that at any dose:

- results in death,
- is life-threatening (i.e., the subject was at risk of death at the time of the event/reaction; it does not refer to an event/reaction which hypothetically might have caused death if it were more severe),
- requires inpatient hospitalization or prolongation of existing hospitalization,

- results in persistent or significant disability/incapacity (where disability is defined as a permanent or substantial disruption of ability to carry out normal life functions, either reported or defined as per clinical judgment),
- is a congenital anomaly/birth defect,
- is an important medical event that may not result in death, be life-threatening, or require hospitalization but may be considered serious when, based upon appropriate medical judgment, it may jeopardize the subject and may require medical or surgical intervention to prevent any of the outcomes listed in the definition above. Examples of such events include allergic bronchospasm requiring intensive treatment in an emergency room or at home, and blood dyscrasias or convulsions that do not result in hospitalization, or development of drug dependency or drug abuse.
- Any suspected transmission via a medicinal product of an infectious agent is also considered a SAE.
- A non-serious adverse event is any adverse event that does not meet the criteria listed above for a SAE.

